Parkinson's disease (PD) is a neurodegenerative disorder that is caused primarily by the loss of dopamine neurons, which reduces the amount of dopamine neurotransmitters. PD presents not only with impairment of motor function and automaticity but also with mild cognitive impairment and attention and working memory deficits¹. PD patients that have a loss of automaticity recruit additional brain networks, specifically the prefrontal areas, even during simple tasks, as a form of compensation². Impairment of the sensorimotor striatum damages automatic control, so PD patients need additional attentional control to perform daily motor behaviors³. A study with functional magnetic resonance imaging (fMRI) showed that, at the automatic stage, specific brain regions (such as the anterior putamen, cerebellum, dorsolateral prefrontal cortex, precentral gyrus, and premotor cortex) are more activated in PD patients than in healthy controls, and the posterior putamen region is more activated in controls than in PD patients⁴. This cognitive compensatory mechanism in PD patients may increase the risk of falls^{5, 6}.

Dual-task (DT) performance is affected by PD. In PD patients, when walking is combined with a cognitive task, spatiotemporal gait parameters worsen⁷; in addition, impaired DT performance has been shown to correlate with an increased risk of falling and diminished quality of life⁸. A previous study showed the occurrence of DT interference during walking in 121 early PD patients and suggested that PD management target DT training in the early stages of PD⁹. There is increasing evidence that integrated or consecutive cognitive-gait DT training improves gait performance¹⁰⁻¹⁶, locomotion automaticity¹⁷, balance, and cognition¹⁶ in patients with PD. However, among the numerous previous DT training studies, only a few studies adopted cycling as a motor task.

Previous studies demonstrated that cycling training improves motor function²⁰⁻²⁴, cognition^{25, 26}, and gait speed^{25, 27} in PD patients. Hazamy et al. indicated that patients with PD showed facilitative effects on cognition while performing a cognitive-cycling DT paradigm²⁸. A recent study found that aerobic cycling training can improve gait speed, single support time during a self-selected speed condition and cognitive performance in PD patients²⁹. We reported that a low-intensity progressive cycling exercise improves motor functions in patients with early-stage PD, especially akinesia. Moreover, the Timed Up and Go (TUG) and double limb support time of these patients significantly decreased after 16 training sessions³⁰.

In summary, previous reports have indicated that DT training improves gait performance and facilitates cognition during a cognitive-cycling DT paradigm in patients with PD. However, only a few DT training studies adopted cycling as a motor task. By advancing our previous study with cycling single-task (ST) training, we aimed to investigate the efficacy of cognitive-cycling DT training in clinically-matched patients with early-stage PD.

OUTCOME MEASURES

The primary outcomes were changes in the results of clinical assessments including the unified Parkinson's disease rating scale part III (UPDRS III) and modified Hoehn and Yahr staging (mHYS) for both off- and on-states, on-state total UPDRS, TUG test, new freezing of gait questionnaire (NFOGQ), Schwab and England Activities of Daily Living (SE-ADL, %), 39-item Parkinson's disease questionnaire (PDQ-39), and spatiotemporal gait performance during a cognitive-walking DT paradigm. Secondary outcomes were changes in cognitive performance and CMI patterns during the cognitive-walking DT paradigm. We measured accuracy and reaction time and computed a composite score that accounted for speed–accuracy trade-offs³¹. Cognitive performance was reported as a composite score (%). DTI of cognitive and motor performances were accounted for by the composite score and gait speed, respectively. Possible adverse events (AE) were recorded during the study.

MATERIAL AND METHODS

Participants

These patients with idiopathic PD were diagnosed by a neurologist specialized in movement disorders according to the diagnostic criteria proposed by Gelb et al.³²

Inclusion Criteria:

- (1) idiopathic Parkinson's disease
- (2) an age between 45 to 70 years
- (3) asymmetrical onset of at least 2 of 3 cardinal sign
- (4) mHYS from 1 to 2.5 during off state
- (5) MoCA score of 26 or greater

Exclusion Criteria: The patients were ineligible if they had

- (1) a neurological history other than PD
- (2) ever undergone neurosurgery for PD
- (3) had moderate to severe dyskinesia
- (4) been unstable with medical or psychiatric co-morbidities, orthopedic conditions restricting exercise
- (5) done more than 20 min of aerobic exercise over 3 sessions per week on their own

Each patient initially received a baseline (pretraining, T0) test and a midterm (T1) test after 8 sessions of the cognitive-cycling DT training. After all 16 sessions of the cognitive-cycling DT training and 2-3 days of a wash-out period, each participant received a posttraining (T2) test.

Clinical assessments

All clinical assessments were performed after 12 hours of overnight withdrawal of anti-Parkinsonian medications. Twenty-four hours of withdrawal was needed for patients taking prolonged-release dopaminergic agonists. The UPDRS III and mHYS assessments were conducted the subsequent morning while patients were in the off state. Each patient self-administered the medications. The total UPDRS, mHYS, TUG test, NFOGQ, SE-ADL, PDQ-39, and spatiotemporal gait analysis were assessed the patients during their best on-state. The UPDRS subscores were analyzed as follows: akinesia (items 23-26; finger taps, hand movements, rapid alternating movements of the hands and leg agility), and PIGD (items 29-30; gait and postural stability).

Intervention

Patients were scheduled to perform cognitive tasks simultaneously with the cycling training twice per week for 8 weeks for a total of 16 sessions during their on-states.

The cycling activity included an initial phase of dose titration for 2 weeks and a late phase of dose maintenance for 6 weeks. Each session included a 5-min warm-up, the main cycling activity and a 5-min cool down. A standard stationary bicycle was used. The cycling activity started with 15 min of a self-selected cadence in the titration phase, and the speed increased by 5 to 10 revolutions per min (rpm) in increments of 5 min. The intensity of cycling reached at least 40 rpm and was maintained for 30 min in the 4th session. The duration for which the intensity was maintained and the total cycling time was extended by 5 min every 4 sessions; the total cycling time was 30 min for 5-8 sessions, 35 min for 9-12 sessions, and 40 min for 13-16 sessions. Blood pressure (BP), heart rate (HR), rating of perceived exertion (RPE, Borg scale)³³, and saturation of peripheral oxygen (SpO₂) were monitored before, during, and after each training session. If an individual's HR exceeded 50~55 % of the individual's target heart rate (THR, defined as 220 minus the individual's age, which is the maximum heart rate using the Karvonen formula)³⁴, the trainer required the patient to decrease his or her cycling cadence to below the THR.

The cognitive activity included an initial phase of 2 weeks and a late phase of 6 weeks. The three cognitive tasks, calculation task, spatial memory task, and Stroop inhibition task, were integrated into the cycling training program. The timing of the cognitive tasks was evenly arranged. During the initial phase, cognitive training started with 15 min, and the same level of complexity was maintained for 4 sessions. During the last phase, the cognitive training time was extended by 5-10 min every 4 sessions; the cognitive training time was 20 min for 5-8 sessions, 30 min for 9-12 sessions, and 35 min for 13-16 sessions. In addition, the complexity of the cognitive tasks was increased progressively every 4 sessions.

Spatiotemporal gait analysis

Gait performance was analyzed using GAITRite (CIR Systems, Inc., Franklin NJ, USA) with a 3.66-meter long and 0.9-meter wide instrumented walkway³⁵ while patients performed the DT paradigm. The DT paradigm comprised four sections: 1) motor single-task (ST), 2) cognitive ST, 3) cognitive-motor DT without task prioritization, and 4) cognitive-motor DT with task-specific prioritization. During the ST cognitive and DT sections, the three cognitive tasks, the calculation, spatial memory, and visual Stroop inhibition tasks, were randomly assigned.

In the motor ST section, the patients were instructed to walk at their “preferred speed” and “fast speed” twice. The outcome measures of the gait assessments were gait speed (cm/sec), step length (cm), step width (cm), step time (sec), and double limb support time (DLST, sec).

In the cognitive ST section, all patients performed three cognitive tasks (i.e., the calculation, spatial memory, and visual Stroop inhibition tasks) while sitting on a chair located approximately 6 meters from a projection screen. The outcomes of cognitive performance were reaction time (millisecond, msec), accuracy (%), and a composite score³¹.

In the cognitive-motor DT section, the patients walked at their preferred speed and simultaneously performed a cognitive task. Three cognitive tasks were each performed twice. No instructions were provided regarding the prioritization of a task. Afterwards, instructions regarding the prioritization of a specific task were provided when patients performed the calculation-walking DT paradigm.

Data analysis

The effect of the DT was described as DTI and calculated as the difference between ST and DT performance expressed as a percentage of ST performance, as follows:

$$\text{Dual-task interference (DTI, \%)} = \frac{\text{DT performance} - \text{ST performance}}{\text{ST performance}} \times 100$$

The cognitive performance was described as a composite score, as follows: Composite score (%) = $\frac{\text{Accuracy} (\%)}{\text{Reaction time (ms)}} \times 100$

Statistics

- 33. Borg GA. Psychophysical bases of perceived exertion. *Med Sci Sports Exerc* 1982;14:377-381.

PRELIMINARY RESULTS

GENERAL INFORMATION

During study period from 2016/06/01 to 2017/05/31, thirteen eligible patients (31 % women) were enrolled and completed the study. The mean age was 60.64 ± 5.32 years (range, 53-67), and the mean age at the onset of PD was 53.62 ± 6.46 years (range, 45-63). The mean disease duration was 7.02 ± 3.23 years (range, 2-14). The mean MoCA test result was 28.69 ± 1.11 (range, 26-30). A total of 12 PD patients completed the training program and all assessments. One subject withdrew from this study due to personal reasons.

OUTCOME MEASURES

The UPDRS III scores improved predominantly from T0 to T2 during both the off- and on-states. Notably, the UPDRS III scores ($p= 0.027$), akinesia subscores ($p= 0.007$), and PIGD subscores ($p= 0.025$) improved significantly from T0 to T1 in the off-state. The observed effect sizes (ES) of the primary outcomes, such as the off-state UPDRS III scores, both the off- and on-states akinesia subscores and the PIGD subscores, TUG, and PDQ-39, were large after 16 sessions of DT training.

While the patients walked at their “preferred speed”, gait speed, step time and double limb support time improved significantly at T1 and T2 compared to T0. Under the calculation-walking DT situation, gait speed, step length, step time, and double limb support time improved significantly at T1 (except step length) and T2 compared to T0. During the spatial memory-walking DT, gait speed and double limb support time improved significantly at T1 (except gait speed) and T2 compared to T0. During the Stroop inhibition-walking DT situation, gait speed, step length, step time, and double limb support time improved significantly at T1 (except step length) and T2 compared to T0. During the DT with prioritization of walking, gait speed, step time, and double limb support time improved significantly at T1 and T2 compared to T0. During the DT with prioritization of the calculation task, gait speed improved significantly at T1 and T2 compared to T0; step time and DLST improved significantly at T2 compared to T0. In summary, gait performance improved significantly after 16 sessions of cognitive-cycling training.

During the cognitive ST and DT sections, the composite score of spatial memory significantly increased at T2 compared to T0.

The adverse events did not recur afterwards.

CONCLUSION

Our study demonstrated that 16 sessions of cognitive-cycling DT training not only improves motor functions of PD patients in off- and on-states but also improves the gait and cognitive performance of PD patients during a DT paradigm. We suggest that cognitive-cycling DT training may be beneficial to include cognitive-cycling DT training as part of the rehabilitation of patients with very early-stage PD.

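### The results call the akinesia and PIGD subscores primary although the primary list omits them, and no test result is given for on-state UPDRS III or on-state total UPDRS behind the on-state motor conclusion

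*Combined protocol and SAP*

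**What the plan says.** The protocol's Outcome Measures section opens its list with "The primary outcomes were changes in the results of clinical assessments including the unified Parkinson's disease rating scale part III (UPDRS III". It takes UPDRS III and mHYS "for both off- and on-states, on-state total UPDRS, TUG test, new freezing of gait questionnaire (NFOGQ", then adds SE-ADL, PDQ-39 and "spatiotemporal gait performance during a cognitive-walking DT paradigm". No subscore is named.

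The subscores enter in the Clinical assessments section: "The UPDRS subscores were analyzed as follows: akinesia (items 23-26", with PIGD defined from items 29-30. That section gives them no place in the outcome hierarchy. The Statistics section assigns the Friedman and Wilcoxon tests to UPDRS III and TUG, and names no test for the subscores.

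The Outcome Measures part of the Preliminary Results then refers to "The observed effect sizes (ES) of the primary outcomes, such as the off-state UPDRS III scores, both the off- and on-states akinesia subscores", continues with PIGD, TUG and PDQ-39, and calls all of these effects large after the full 16 sessions. No numerical effect size is given. The Conclusion states that the training "not only improves motor functions of PD patients in off- and on-states", and adds gait and cognitive performance as a further finding.

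**The concern.** Two things do not line up. First, the results give primary status to measures that the list does not name, while several measures that it does name are not reported. Second, the on-state half of the motor conclusion has no reported test on either listed on-state UPDRS score.

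With 12 completers, many primary readings and no multiplicity adjustment described, a reader relies on the declared list to tell planned endpoints from selected ones. If the label moves to other measures once results are known, the reader loses that protection and cannot tell how the listed on-state motor scores behaved.

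**Working it through.** The documents state no sample size calculation and no numerical effect size, so there is no design figure to reproduce. The check compares the sections with one another.

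**Step 1. Listed clinical primaries, counted by state (Outcome Measures).** UPDRS III off and on (2), mHYS off and on (2), on-state total UPDRS (1), TUG (1), NFOGQ (1), SE-ADL (1), PDQ-39 (1): 2 + 2 + 1 + 1 + 1 + 1 + 1 = 9. Gait is listed in addition.

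**Step 2. Readings called primary in the effect-size sentence (Preliminary Results).** Off-state UPDRS III (1), akinesia off and on (2), PIGD in one or both states (1 or 2, as the wording is ambiguous), TUG (1), PDQ-39 (1): 6 or 7.

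**Step 3. Overlap.** Off-state UPDRS III, TUG and PDQ-39 are on the list: 3. Not on the list: 6 − 3 = 3, or 7 − 3 = 4.

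**Step 4. What is reported for the nine listed readings.**

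| Listed reading | Result in the document |
|---|---|
| UPDRS III, off | p = 0.027 (T0 to T1); large effect, no figure |
| UPDRS III, on | said to improve T0 to T2; no test, no effect size |
| mHYS, off | none |
| mHYS, on | none |
| Total UPDRS, on | none |
| TUG | large effect, no figure, no p-value |
| NFOGQ | none |
| SE-ADL | none |
| PDQ-39 | large effect, no figure, no p-value |

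Five of nine have no result, and a sixth has direction only.

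**Step 5. UPDRS p-values.** There are three: UPDRS III 0.027, akinesia 0.007, PIGD 0.025. All are off-state and T0 to T1. Two of the three are subscores. None is on-state, and none covers T0 to T2.

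**Step 6. Reported support for on-state motor improvement.**
- UPDRS III: an untested statement of improvement.
- Akinesia and, on the natural reading, PIGD: unquantified large effects, no p-value, not on the primary list.
- TUG: a listed primary measured in the best on-state, with an unquantified large effect and no p-value.
- Gait: listed, and also on-state ("PDQ-39, and spatiotemporal gait analysis were assessed the patients during their best on-state"), with several parameters significantly better at T1 and T2. This includes walking at preferred speed, which belongs to the paradigm because "The DT paradigm comprised four sections: 1) motor single-task (ST), 2) cognitive ST". The Conclusion reports gait as a separate finding from motor function.

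**Illustration only.** With independent tests at 0.05 and no true effects, the chance of at least one false positive is 1 − 0.95^9 = 0.370 for nine readings. With both subscores added in both states (13 readings) it is 1 − 0.95^13 = 0.487. These scales are correlated, so the figures do not describe this trial. They show only why the length of a primary list matters.

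**The case against.** The best defence is that the subscores were not invented after the fact. The primary list is introduced by a word that leaves it open, the methods define both subscores by item number, and the Introduction says that the team's previous cycling study helped akinesia in particular. The effect-size sentence also presents its measures as examples, not as a full list. This stands in part: the subscores are unranked components of a listed scale, not measures absent from the methods. It does not make them primary. The list goes down to named instruments and, for UPDRS III, mHYS and total UPDRS, to medication state, so a subscore meant as primary would be expected there.

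A reader might go further and infer that the on-state conclusion depends on the subscores, or that they were substituted because the full scale showed less. The documents do not support either reading. The on-state subscores have no significance result, so they are no firmer than TUG, which is listed and has the same kind of effect-size statement. Listed on-state gait results are significant. No on-state UPDRS III effect size is given, so its omission may suggest a smaller effect but cannot establish one. In the off-state, the full UPDRS III stands beside its subscores with its own p-value and large effect, so nothing was replaced there.

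It would also be wrong to say that the on-state claim can stand only on UPDRS III, because the documents do not define motor function as that score alone.

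**Conclusion.** The point holds as a labelling and reporting fault. Two subscores outside the primary list are called primary, and they account for three or four of the six or seven readings in that sentence. Five of the nine listed clinical readings have no reported result. On-state UPDRS III has no test, on-state total UPDRS has no result at all, and yet motor improvement is concluded for both states.

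The on-state claim is under-documented, not shown to be false. The reported support for it is one untested UPDRS statement, unquantified effects for TUG and for unlisted subscores, and gait, which the Conclusion counts separately.

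The counts assume that each medication state is a separate reading and that gait is left out of the nine. The only ambiguity is whether PIGD is meant in one state or both, and that does not change the conclusion. The fault should be corrected because it bears on a stated conclusion and costs little to put right.

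**What to change.** 1. In the Preliminary Results, take akinesia and PIGD out of the sentence on primary outcomes, and report them as UPDRS subscores that were not on the primary list. Do not write a new rank for them into the methods now, because the results are known.
2. Add a table with the T0 to T2 estimate, effect size and p-value for every listed primary, by state where it was measured in both. Include null results and the readings now missing or incomplete: on-state UPDRS III, on-state total UPDRS, mHYS in both states, NFOGQ and SE-ADL. State the test used for each one that the Statistics section does not cover.
3. In the Conclusion, name the listed on-state endpoint or endpoints that support the motor claim (for example TUG, if its test is significant). Say plainly if on-state UPDRS III or total UPDRS did not change significantly.

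This needs one table from data already collected and a few changed sentences. The downside is a possibly less favourable on-state headline.
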